**Acronyms**

CR	Calorie restriction
IF	Intermittent fasting
SC	Standard care
AUSDRISK	Australian type 2 diabetes risk assessment tool
PAS	Primary analysis set
FAS	Full analysis set
FinAS	Final (week 76) analysis set
SAS	Safety analysis set

### **Hypothesis**

Intermittent fasting (IF) would produce superior glycemic benefits than daily calorie restriction (CR) at 6 months post-intervention.

### **Study Design Change**

*Changes made prior to 2nd Interim Analysis – accepted by the DMC. Primary investigator (LH) was blinded to the results of interim analysis 1.*

Given the interruption due to COVID-19 it was considered ill advised to continue accrual. Regarding study design, the study team chose to consider change in glucose control as the single primary outcome and change in HbA1c as a secondary outcome, with no further interim analyses (for efficacy).

The original design had HbA1c and glucose AUC as dual primary endpoints and envisaged 3 interim analyses (at N/6, N/3 and N/2), with a multiple testing adjusted two-sided alpha=0.05 (ie two-sided alpha=0.025 for each endpoint). Assuming 25% attrition a N=260 would provide at least 80% power for the HbA1c endpoint and >90% power for the glucose AUC endpoint.

With this new design and assuming 25% attrition and a pre-post correlation of 0.4, then a sample size of N=208 (83:83:42 in the three arms) provides at least 85% power to detect a mean difference of 0.4 mmol/h (SD=0.8) in glucose AUC between the two active interventions (two-sided alpha=0.04999992).

*At the first interim analysis (N/6) negligible alpha was spent. Assuming trial could stop for a Type I error in either outcome 6.3e-07 was spent (gsDesign).*

### **Primary Outcome Measures**

- (Planned) Dual HbA1c and post-prandial glucose AUC
- (Final) Post-prandial glucose AUC

### **Primary comparison**

- Between CR and IF at week 24

### **Randomization**

- Stratified blocked randomisation according to a 2:2:1 ratio (CR:IF:SC)
- Block length 3 or 6
- Stratification factors: Sex (F vs M) & AUSDRISK (12-19 vs 20+)

**Cohorts**

Primary Analysis Set (PAS) includes all individuals with a week 24 post-prandial glucose assessment. Individuals are included in the groups they were allocated to at randomization.

[figure not shown]
Full Analysis Set (FAS) includes all individuals randomized in the groups they were allocated to at randomization with at least one post baseline week 8 or week 24 assessment.

Final Analysis Set (FinAS) includes all individuals randomized in the groups they were allocated to at randomization with the week 76 assessment.

Safety Analysis Set (SAS) includes all individuals randomized in the groups they were allocated to.

**Outcomes**

*Efficacy Measures*

	baseline	8A	24A	76A
Diet/Behaviour				
Total energy intake	•	•	•	•
Carbohydrate intake	•	•	•	•
Protein intake	•	•	•	•
Fat intake	•	•	•	•
Fibre intake	•	•	•	•
Physical activity (steps count)	•	•	•	•
Weight Loss Measures				
Body weight (fasting)*	•	•	•	•
Waist circumference	•		•	•
Hip circumference	•		•	•
fat mass	•		•	•
fat free mass	•		•	•
Diabetes Measures				
Postprandial glucose AUC	•		•	•
HbA1c	•	•	•	•
Fasting glucose	•	•	•	•
Fasting insulin	•	•	•	•
Fasting NEFA	•	•	•	•
Fasting triglyceride	•	•	•	•
Postprandial insulin	•		•	•
Postprandial NEFA	•		•	•
Postprandial triglyceride	•		•	•
Clinical Outcomes				
Systolic blood pressure	•	•	•	•
Diastolic blood pressure	•	•	•	•
LDL	•	•	•	•
HDL	•	•	•	•
Cholesterol	•	•	•	•
hsCRP	•	•	•	•

\* Non fasting weight also reported every two weeks, with fasting weight assessed as above.

*Adverse Event Measures*

- The maximum grade of adverse events will be calculated per individual per event category per time period (weeks 1-24 and weeks 25-76).
- Counts and percentages will be presented for each treatment group and overall.
- For each category and assessment period, the number of individuals will be compared between groups when there are at least 4 individuals with an event.
- Summaries and comparisons will also be performed for only adverse events that are considered at least *possibly related* to the intervention.

**Data Presentation - Outcomes**

All efficacy outcomes will have mean (SD) and median (IQR) reported for all treatment groups at all assessment times and change from baseline at post baseline assessments.

Cohort: FAS

Table: Measured outcomes at four visits (Baseline = Week 0, Visit 1 = Week 8, Visit 2 = Week 24, and Visit 3 = Week 76).

		Baseline*	Visit 1	Visit 2	Visit 3
Outcome 1					
Group 0	Mean (SD)	XX (YY)	XX (YY)	XX (YY)	XX (YY)
	Median [IQR]	XX [XY, ZZ]	XX [XY, ZZ]	XX [XY, ZZ]	XX [XY, ZZ]
	N (%)	XX (YY %)	XX (YY %)	XX (YY %)	XX (YY %)
Group 1	Mean (SD)	XX (YY)	XX (YY)	XX (YY)	XX (YY)
	Median [IQR]	XX [XY, ZZ]	XX [XY, ZZ]	XX [XY, ZZ]	XX [XY, ZZ]
	N (%)	XX (YY %)	XX (YY %)	XX (YY %)	XX (YY %)
Group 2	Mean (SD)	XX (YY)	XX (YY)	XX (YY)	XX (YY)
	Median [IQR]	XX [XY, ZZ]	XX [XY, ZZ]	XX [XY, ZZ]	XX [XY, ZZ]
	N (%)	XX (YY %)	XX (YY %)	XX (YY %)	XX (YY %)
Outcome 2					
Group 0	Mean (SD)	XX (YY)	XX (YY)	XX (YY)	XX (YY)
	Median [IQR]	XX [XY, ZZ]	XX [XY, ZZ]	XX [XY, ZZ]	XX [XY, ZZ]
	N (%)	XX (YY %)	XX (YY %)	XX (YY %)	XX (YY %)
Group 1	Mean (SD)	XX (YY)	XX (YY)	XX (YY)	XX (YY)
	Median [IQR]	XX [XY, ZZ]	XX [XY, ZZ]	XX [XY, ZZ]	XX [XY, ZZ]
	N (%)	XX (YY %)	XX (YY %)	XX (YY %)	XX (YY %)
Group 2	Mean (SD)	XX (YY)	XX (YY)	XX (YY)	XX (YY)
	Median [IQR]	XX [XY, ZZ]	XX [XY, ZZ]	XX [XY, ZZ]	XX [XY, ZZ]
	N (%)	XX (YY %)	XX (YY %)	XX (YY %)	XX (YY %)

\*When more than one baseline assessment has occurred for some individuals, the within-individual means will be used.

Table: Change from baseline\* outcomes at the three post-baseline visits.

		Visit 1	Visit 2	Visit 3
Outcome 1				
Group 0	Mean (SD)	XX (YY)	XX (YY)	XX (YY)
	Median [IQR]	XX [XY, ZZ]	XX [XY, ZZ]	XX [XY, ZZ]
	N (%)	XX (YY %)	XX (YY %)	XX (YY %)
Group 1	Mean (SD)	XX (YY)	XX (YY)	XX (YY)
	Median [IQR]	XX [XY, ZZ]	XX [XY, ZZ]	XX [XY, ZZ]
	N (%)	XX (YY %)	XX (YY %)	XX (YY %)
Group 2	Mean (SD)	XX (YY)	XX (YY)	XX (YY)
	Median [IQR]	XX [XY, ZZ]	XX [XY, ZZ]	XX [XY, ZZ]
	N (%)	XX (YY %)	XX (YY %)	XX (YY %)
Outcome 2				
Group 0	Mean (SD)	XX (YY)	XX (YY)	XX (YY)
	Median [IQR]	XX [XY, ZZ]	XX [XY, ZZ]	XX [XY, ZZ]
	N (%)	XX (YY %)	XX (YY %)	XX (YY %)
Group 1	Mean (SD)	XX (YY)	XX (YY)	XX (YY)
	Median [IQR]	XX [XY, ZZ]	XX [XY, ZZ]	XX [XY, ZZ]
	N (%)	XX (YY %)	XX (YY %)	XX (YY %)
Group 2	Mean (SD)	XX (YY)	XX (YY)	XX (YY)
	Median [IQR]	XX [XY, ZZ]	XX [XY, ZZ]	XX [XY, ZZ]
	N (%)	XX (YY %)	XX (YY %)	XX (YY %)

\*When more than one baseline assessment has occurred for some individuals, the within-individual means will be used.

**Primary Outcome Comparison**

Objective: Week 24 post-prandial glucose AUC for CR and IF groups.

Cohort: PAS

Linear regression model:  $Y \sim \text{Group (CR v IF)} + \text{Sex (M v F)} + \text{AUSDRISK} + Y0$

- $Y$  = Post prandial glucose;  $Y0$  = Baseline post prandial glucose assessment
- AUSDRISK and  $Y0$  included as a continuous linear variables.
- Missing baseline covariate data are assumed to be infrequent and imputed using cohort means.
- Significance is one-sided  $p < 0.04999992$  (two-sided).

	Est [95%CI]	p-value
IF v CR	XX [YY, ZZ]	PP

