**Secondary Analyses (week 24)**

The primary outcome and all other efficacy outcomes with week 8 and 24 assessments will be analysed using repeated measures with a random intercept per individual. Efficacy outcomes without a week 8 will be analysed using linear regression of week 24 data only. The FAS cohort will be used, with individuals with no post baseline assessment for each outcome excluded per analysis. Missing baseline covariate data are assumed to be infrequent and imputed using cohort means.

Estimates and 95% CIs will be reported per group for all assessments (restricted maximum likelihood estimates), however pairwise comparisons will only be assessed if the overall effect of Group is significant (likelihood ratio test of nested models with/without Group). Significance will be considered at  $p < 0.05$  (two-sided) with no adjustment for multiple testing and conclusions interpreted as exploratory.

Cohort: FAS

Model (wk 8):  $Y \sim \text{Visit} + \text{Group} + \text{Visit} \times \text{Group} + \text{Sex (M v F)} + \text{AUSDRISK} + Y0 + (1 | \text{ID})$

Model (no wk 8):  $Y \sim \text{Group} + \text{Sex (M v F)} + \text{AUSDRISK} + Y0$

- Y = Week 8 and 24 assessments where available per outcome (see pg 4)
- Y0 = Baseline assessment
- Visit = week 8 and 24.
- Group: CR vs IF vs SC.
- AUSDRISK and Y0 included as a continuous linear variables.

Visual inspection of residual and random effect distributions will be undertaken. If residual distributions appear not satisfactory then log transformations will be applied and if still not satisfactory GLMMs will be considered with different error distributions.

	Group p-value	Visit (wk 8)		Visit (wk 24)	
		Est [95%CI]	p-value*	Est [95%CI]	p-value*
Outcome 1 (with wk8)					
CR v SC	PP	XX [YY, ZZ]	PP	XX [YY, ZZ]	PP
IF v SC		XX [YY, ZZ]	PP	XX [YY, ZZ]	PP
IF v CR		XX [YY, ZZ]	PP	XX [YY, ZZ]	PP
Outcome 2 (no wk 8)					
CR v SC	PP			XX [YY, ZZ]	PP
IF v SC				XX [YY, ZZ]	PP
IF v CR				XX [YY, ZZ]	PP

\*Only reported if the overall Group test is significant ( $p < 0.05$ ).

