**Bayesian Joint Secondary Analysis of Postprandial Glucose and HbA1c**

The posterior probabilities of the between group difference in HbA1c for CR vs IF, and for SC vs IF+CR combined will be calculated using a sceptical bivariate Gaussian normal prior. This prior will be mean centred and with covariance

$$\Sigma = \begin{bmatrix} 0.14 & 0.08115171 \\ 0.08115171 & 0.096 \end{bmatrix},$$

corresponding to a correlation of 0.7 and variance of 0.14 for HbA1c and 0.15 for post-prandial glucose AUC. (Note there is an error in the protocol paper Teong et al 2020 where the post-prandial glucose variance was reported as 1.5 across standardized mean differences in historical studies. Converting to units of mmol/h we assume a SD of 0.8.)

We assume that observations from individuals in this study are exchangeable under the prior.

This analysis uses the PAS cohort.

To mimic the study design, the posteriors will be calculated in two stages: (A) initially including individuals used in the interim analysis and (B) then the subsequently randomized individuals. Each stage calculates the likelihood for the between group mean difference in the within-individual change from baseline values, assumed to be normally distributed with known variance. The posterior from the first stage is included as the prior for the second stage.

Reported will be

1. The mean and co-variance matrix for the posterior distribution
2. The probability that the change in HbA1c for
  - a. IF vs CR is less than -0.3%, and vice versa.
  - b. IF+CR vs SC is less than -0.3%.
3. The probability that the change in postprandial glucose AUC for
  - a. IF vs CR is less than -0.4 mmol/h and vice versa.
  - b. IF+CR vs SC is less than -0.4 mmol/h.
4. The joint probability that for IF+CR vs SC
  - a. Either HbA1c is less than -0.3% or postprandial glucose AUC is less than -0.4 mmol/h.
  - b. Both HbA1c is less than -0.3% and postprandial glucose AUC is less than -0.4 mmol/h.

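### The primary significance rule is labelled both one-sided and two-sided; the design calculation shows that two-sided is meant

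*SAP*

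**What the plan says.** The SAP section Primary Outcome Comparison compares week 24 post-prandial glucose AUC between IF and CR by linear regression. The model adjusts for sex, AUSDRISK and the baseline value. The decision rule is "Significance is one-sided $p < 0.04999992$ (two-sided"), and the results table beneath it reports an estimate, a 95% confidence interval and a p-value for IF v CR.

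The section Study Design Change gives the same threshold in the power statement for the revised design, as the level for the comparison "between the two active interventions (two-sided alpha=0.04999992"). It describes the superseded dual-endpoint design as having "two-sided alpha=0.05 (ie two-sided alpha=0.025 for each endpoint").

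The week 24 and week 76 secondary analyses are tested at p < 0.05, marked two-sided. The Hypothesis section is directional: it expects IF to be better than CR. No section sets a one-sided alpha.

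**The concern.** The sentence gives two incompatible rules at one threshold. A two-sided rule at 0.04999992 leaves about 2.5% for a false claim in favour of IF. A one-sided rule at the same number leaves about 5% for that claim and none for a finding in favour of CR. The total type I error is near 5% either way, but the error in the direction the trial hopes to show doubles.

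The affected results are those that favour IF with a two-sided p between about 0.05 and 0.10: a success under one label and a failure under the other. If the one-sided label were followed, superiority could be claimed beside a 95% confidence interval that includes zero, in the same table. The SAP should leave no such choice open once the data are seen.

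**Working it through.** **Inputs**, all from the SAP section Study Design Change: difference 0.4 mmol/h; SD 0.8; pre-post correlation 0.4; 83 randomised to each active arm; 25% attrition; alpha 0.04999992. Lower AUC is better, so a negative IF minus CR difference favours IF. The normal approximation is used unless stated.

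**Step 1. Standard error under the planned model**
- Completers per arm: 83 × 0.75 = 62.25, taken as 62.
- Baseline-adjusted residual SD: 0.8 × √(1 − 0.4²) = 0.7332.
- SE of the difference: 0.7332 × √(2/62) = 0.1317.

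**Step 2. Reproduce the plan's power figure.** The plan says that the design "provides at least 85% power to detect a mean difference of 0.4 mmol/h (SD=0.8) in glucose AUC". The standardised effect is 0.4 / 0.1317 = 3.037.

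| Reading of 0.04999992 | Critical z | Power, normal | Power, noncentral t |
|---|---|---|---|
| Two-sided | 1.960 | Φ(3.037 − 1.960) = 85.9% | 85.4% |
| One-sided | 1.645 | Φ(3.037 − 1.645) = 91.8% | 91.6% |

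The two-sided reading sits just above the stated minimum; the one-sided reading overshoots it by almost 7 percentage points.

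**Step 3. Work back from 85% power.** Completers per arm = 2 × (z_α + 1.036)² × 0.7332² / 0.4².

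| Reading | Completers per arm | Randomised per arm (÷ 0.75) | Total at 2:2:1 (× 2.5) |
|---|---|---|---|
| Two-sided | 61 | 82 | 205 |
| One-sided | 49 | 66 | 165 |

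The planned 208 (83:83:42) fits the two-sided reading.

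**Step 4. Sensitivity to the SD.** If the correlation is ignored and the raw SD of 0.8 is used with 62 completers, power is 79.5% two-sided and 87.3% one-sided. Only that route makes a one-sided test look like 85%, and it discards both the stated correlation and the stated two-sided alpha.

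**Step 5. Where the two rules disagree**
- One-sided critical difference: −1.645 × 0.1317 = −0.217 mmol/h.
- Two-sided critical difference: −1.960 × 0.1317 = −0.258 mmol/h.
- Example at −0.24: z = −1.82, one-sided p = 0.034, two-sided p = 0.068, 95% CI −0.24 ± 0.258 = −0.498 to 0.018.

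The probability that the estimate falls between −0.258 and −0.217 depends on the true difference:

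| True IF minus CR (mmol/h) | Probability |
|---|---|
| 0 | 2.5% |
| −0.2 | 12.0% |
| −0.4 | 5.9% |

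**The case against.** The strongest reply is that the document largely settles the question itself. The disputed sentence ends with the label two-sided, the design section attaches "two-sided alpha=0.04999992" to the power statement, and no section sets a one-sided level. An analyst would have to disregard all of that to run a one-sided test. This stands, and it limits the weight of the point: it is a wording error, not a flaw in the design or a threat to the trial's validity.

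Some of the surrounding evidence is also weaker than it looks. A two-sided interval can accompany a one-sided test. The two-sided labels in the secondary sections govern analyses described as "with no adjustment for multiple testing and conclusions interpreted as exploratory". The Bayesian section looks at both directions ("IF vs CR is less than -0.4 mmol/h and vice versa"), but posterior probabilities do not fix the sidedness of a frequentist test. These are consistent with the two-sided reading without proving it; the design section carries the argument and is enough.

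The directional hypothesis is the one item that could explain the word one-sided. It does not justify it: a directional hypothesis can be tested two-sided, and the design section chose two-sided explicitly.

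A separate matter is the threshold value. The design section says "Assuming trial could stop for a Type I error in either outcome 6.3e-07 was spent (gsDesign"), whereas 0.05 − 0.04999992 = 8e-08; simple subtraction of the stated spend would give 0.04999937. The calculation may not have been simple subtraction, and the practical effect is nil. It has no bearing on the one-sided or two-sided question.

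**Conclusion.** The contradiction is real and should be corrected. The primary decision rule is wrong as written, and the plan's own sample size identifies the stray word: power and total N reproduce two-sided (85.9%, 205 against the planned 208) and not one-sided (91.8%, 165).

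The consequence is confined to results favouring IF with a two-sided p between about 0.05 and 0.10. That limit on the p-value holds whatever the SD. The range in mmol/h and the probabilities of falling in it rest on the planning SD, correlation and attrition and on the normal approximation, and would shift with the observed variability and number of completers.

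**What to change.** In the SAP section Primary Outcome Comparison, delete the word one-sided and state the rule once, as two-sided p < 0.04999992, in agreement with Study Design Change. The correction concerns sidedness only. While the line is open, a short note on how the threshold follows from the alpha spent at the first interim analysis would also settle the 8e-08 against 6.3e-07 question. The cost is a one-word edit, with no new data, participants or analyses and no change to the sample size or power statement.

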**Secondary Analyses (week 24)**

The primary outcome and all other efficacy outcomes with week 8 and 24 assessments will be analysed using repeated measures with a random intercept per individual. Efficacy outcomes without a week 8 will be analysed using linear regression of week 24 data only. The FAS cohort will be used, with individuals with no post baseline assessment for each outcome excluded per analysis. Missing baseline covariate data are assumed to be infrequent and imputed using cohort means.

Estimates and 95% CIs will be reported per group for all assessments (restricted maximum likelihood estimates), however pairwise comparisons will only be assessed if the overall effect of Group is significant (likelihood ratio test of nested models with/without Group). Significance will be considered at  $p < 0.05$  (two-sided) with no adjustment for multiple testing and conclusions interpreted as exploratory.

Cohort: FAS

Model (wk 8):  $Y \sim \text{Visit} + \text{Group} + \text{Visit} \times \text{Group} + \text{Sex (M v F)} + \text{AUSDRISK} + Y0 + (1 | \text{ID})$

Model (no wk 8):  $Y \sim \text{Group} + \text{Sex (M v F)} + \text{AUSDRISK} + Y0$

- Y = Week 8 and 24 assessments where available per outcome (see pg 4)
- Y0 = Baseline assessment
- Visit = week 8 and 24.
- Group: CR vs IF vs SC.
- AUSDRISK and Y0 included as a continuous linear variables.

Visual inspection of residual and random effect distributions will be undertaken. If residual distributions appear not satisfactory then log transformations will be applied and if still not satisfactory GLMMs will be considered with different error distributions.

	Group p-value	Visit (wk 8)		Visit (wk 24)	
		Est [95%CI]	p-value*	Est [95%CI]	p-value*
Outcome 1 (with wk8)					
CR v SC	PP	XX [YY, ZZ]	PP	XX [YY, ZZ]	PP
IF v SC		XX [YY, ZZ]	PP	XX [YY, ZZ]	PP
IF v CR		XX [YY, ZZ]	PP	XX [YY, ZZ]	PP
Outcome 2 (no wk 8)					
CR v SC	PP			XX [YY, ZZ]	PP
IF v SC				XX [YY, ZZ]	PP
IF v CR				XX [YY, ZZ]	PP

\*Only reported if the overall Group test is significant ( $p < 0.05$ ).

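### The week 8/24 secondary model forces the same variance at both visits; if spread differs, the visit-specific confidence intervals are miscalibrated, and one extra covariance parameter prevents this

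*SAP*

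**What the plan says.** The SAP section Secondary Analyses (week 24) states that outcomes with both post-baseline visits "will be analysed using repeated measures with a random intercept per individual". The model has Visit, Group, their interaction, sex, AUSDRISK and baseline as fixed effects, and (1 | ID) as its only random term. No visit-specific residual variance, unstructured covariance or robust standard error is named.

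On reporting, the section says "Estimates and 95% CIs will be reported per group for all assessments", estimated by REML, and that "pairwise comparisons will only be assessed if the overall effect of Group is significant". The table has separate columns for weeks 8 and 24. The footnote "Only reported if the overall Group test is significant" is attached to the p-value columns only. Significance is two-sided at 0.05, "with no adjustment for multiple testing and conclusions interpreted as exploratory".

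The model check is visual: "If residual distributions appear not satisfactory then log transformations will be applied and if still not satisfactory GLMMs will be considered". Under Data Presentation - Outcomes, "All efficacy outcomes will have mean (SD) and median (IQR) reported for all treatment groups at all assessment times", so SDs by visit will be seen, but no rule links them to the choice of covariance model.

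The scope is limited: "Efficacy outcomes without a week 8 will be analysed using linear regression of week 24 data only". That includes postprandial glucose AUC, which has no week 8 assessment in the Outcomes table.

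**The concern.** A random intercept with a single residual variance is compound symmetry. It gives each visit the same variance (between-person plus residual) and uses the between-person part as the covariance. The two visits therefore share one pooled variance, although the table reports a contrast, an interval and a p-value at each.

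If people spread apart between week 8 and week 24, the pooled variance is too small for week 24 and too large for week 8. If spread shrinks, the reverse holds. The affected outcomes include HbA1c, which was a dual primary endpoint before the design change. What is at stake is whether a nominal 95% interval for a between-group difference at a given visit covers 95% of the time, and whether the pairwise p-values hold their level.

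**Working it through.** **The plan's own figure.** The SAP states no figure for this model. Its only computable design figure is the primary power of at least 85%. With 83 x 0.75 = 62 per active arm, a difference of 0.4 mmol/h, SD 0.8 x sqrt(1 - 0.4²) = 0.733 and two-sided alpha 0.04999992, power is 85.9% (normal) or 85.4% (noncentral t). That reproduces the statement, and it supplies the arm sizes used below: 62, 62 and 31, from 83:83:42 less 25%.

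**Scope, from the Outcomes table.** With a week 8 assessment: 6 diet/behaviour + 1 fasting weight + 5 diabetes + 6 clinical = 18. Without: 4 body measures + 4 postprandial = 8. Total 26.

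**Closed form.** Let s8 and s24 be the SDs at the two visits given the covariates, and r = s24/s8. With complete data the fitted common variance is about (s8² + s24²)/2. Hence

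- model SE / true SE at week 24 = sqrt((s8² + s24²)/2) / s24, and with s8 in the denominator at week 8;
- coverage = 2Φ(1.96 x ratio) - 1; unscreened error = 1 - coverage.

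Example, r = 1.5: (1 + 2.25)/2 = 1.625; sqrt = 1.275; 1.275/1.5 = 0.850; 1.96 x 0.850 = 1.666; coverage 90.4%, error 9.6%.

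| r (assumed) | Week 24 SE ratio | Week 24 coverage | Week 24 unscreened error | Week 8 SE ratio | Week 8 coverage |
|---|---|---|---|---|---|
| 1.0 | 1.000 | 95.0% | 5.0% | 1.000 | 95.0% |
| 1.1 | 0.956 | 93.9% | 6.1% | 1.051 | 96.1% |
| 1.25 | 0.906 | 92.4% | 7.6% | 1.132 | 97.3% |
| 1.5 | 0.850 | 90.4% | 9.6% | 1.275 | 98.8% |
| 2.0 | 0.791 | 87.9% | 12.1% | 1.581 | 99.8% |

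For r = 0.9 or 0.8 the excess moves to week 8, with error 6.2% or 7.6%.

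**Simulation with the overall Group test in place.** Complete data at 62/62/31; planned fixed effects; assumed between-visit correlation 0.6 given covariates; 60,000 runs per scenario (Monte Carlo SE about 0.1 point). The Group test was an ML likelihood ratio test on 4 df (Group and Visit x Group). Pairwise t tests used n - 9 df as a stand-in for Satterthwaite. Diet effects were equal for CR and IF, in units of each visit's own SD, so any IF v CR claim is false. Simulated week 24 coverage of the planned model with no group differences was 95.0/93.9/92.6/90.8/88.2% across the five ratios, against 95.0 to 95.2% for the unstructured model.

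| Error after the Group test | r = 1.0 | 1.1 | 1.25 | 1.5 | 2.0 | Unstructured, all r |
|---|---|---|---|---|---|---|
| No differences: IF v CR, week 24 | 1.8% | 2.2% | 2.8% | 3.5% | 4.5% | – |
| No differences: any false pairwise claim (3 pairs, 2 visits) | 5.1% | 5.3% | 5.6% | 6.5% | 7.8% | 4.9–5.2% |
| Both diets 0.2 SD from SC: IF v CR, week 24 | 2.4% | 3.0% | 3.7% | 5.0% | 6.2% | 2.4–2.5% |
| Both diets 0.4 SD from SC: IF v CR, week 24 | 3.8% | 4.7% | 6.0% | 7.4% | 9.6% | 3.7–4.0% |
| Both diets 0.8 SD from SC: IF v CR, week 24 | 5.0% | 6.0% | 7.3% | 9.3% | 11.8% | 4.9–5.0% |

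The Group test was passed in 13–17%, 40–47% and 96–97% of runs at 0.2, 0.4 and 0.8 SD. The larger the shared diet effect, the less it protects IF v CR.

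**Sensitivity.**

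- Attrition (83/83/42 at week 8, 62/62/31 at week 24, random dropout, 4,000 runs, Monte Carlo SE about 0.35 point near 5%): at 0.4 SD and r = 1.0/1.25/1.5/2.0, IF v CR error was 4.4/6.6/8.2/12.5% under the planned model and 4.3/4.2/3.6/4.3% unstructured.
- Effect fixed in week 8 SD units: the planned Group test also detects true effects less often. At r = 1.25/1.5/2.0 it passed in 32/26/19% of runs against 35/33/33% unstructured (0.4 SD), and in 90/82/62% against 92/91/91% (0.8 SD).
- A separate simulation (arms of 32, 66 and 66, 15% missing at week 24, 1,000 runs) moved week 24 coverage, from random intercept to unstructured, from 91.8 to 95.7% (r = 1.25), 89.7 to 95.1% (1.5) and 87.3 to 95.6% (2.0). At r = 1.0 it was 94.4 and 94.6%.

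**The case against.** The best reply is that no error has been demonstrated. The model is complete and conventional, the SAP gives no SD by visit, and nothing in it makes a ratio of 1.5 or 2.0 more likely than 1.0. If spread shrinks, the week 24 intervals are conservative. The unscreened error rates are not those of the planned p-value procedure: with no group differences at all, the Group test keeps the week 24 IF v CR error at or below 4.5% even at a ratio of 2.0. Residuals will be inspected, SDs will be shown by visit, and everything here is exploratory and unadjusted across 18 outcomes. For two-weekly non-fasting weight, the section Weekly weight assessments already uses random slopes, which let spread change over time.

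Much of this stands, and it sets the weight of the point. The size and direction of any inequality are unknown, and at a ratio of 1.1 the excess is about one point or less. Four parts of the reply do not remove the concern:

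- The table footnote restricts p-values, not intervals, and the Group test protects IF v CR poorly when both diets clearly differ from SC.
- A log scale or GLMM can help where variance follows the mean, but neither frees it by visit independently of the mean.
- An exploratory label does not make an under-covering 95% interval acceptable.
- The random slopes apply only to the two-weekly weights; fasting weight at weeks 8 and 24 is still analysed with a random intercept alone.

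The calculations show no problem with degrees of freedom as such: coverage at a ratio of 1.0 is 95.0%.

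**Conclusion.** The concern holds, as a conditional and minor one. The planned covariance rules out unequal spread at weeks 8 and 24 in 18 of 26 outcome analyses, and no planned step relaxes that. If the visit SDs differ by a quarter, the interval at the more variable visit covers about 92.4%; at a ratio of 1.5, about 90.4%; with equal SDs there is no error. After the Group test, any false pairwise claim with no group differences reaches 6.5 to 7.8% at ratios of 1.5 to 2.0, and the IF v CR error depends on how far both diets differ from SC.

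All SD ratios, effect sizes and the correlation of 0.6 are assumptions. The primary comparison, the 8 outcomes without week 8 and the week 76 analysis use single-visit regression and are not touched.

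**What to change.** In Secondary Analyses (week 24), replace (1 | ID) with an unstructured 2x2 within-person covariance by visit, or equivalently allow visit-specific residual variances. Fit it by REML with Kenward-Roger or Satterthwaite degrees of freedom, and use the same covariance structure in the ML likelihood ratio test of Group. Keep the fixed effects, the Group test and the exploratory label as they are. This covers the Gaussian model on the original or log scale; if a GLMM is used, its within-person structure needs its own statement.

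The cost is one covariance parameter (three instead of two), with no extra data or patients. At equal variances the mean week 24 standard error was the same under both models (0.181 with complete data, 0.172 with attrition), and the rates of passing the Group test agreed within 0.4 points.
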